## 6.5 EFFICACY ANALYSES

Efficacy variables assessed in the study will include:

- OS (defined in Section 2.1)
- HRQoL, as assessed by QLQ-C30 questionnaire
- PFS (defined in Section 2.1)
- ORR (defined in Section 2.1)
- DCR (defined in Section 2.1)
- DoR (defined in Section 2.1)
- Utilities collected using the EQ-5D-5L for pharmacoeconomic models

Further exploratory efficacy endpoints might also be considered, as applicable.

The intent-to-treat (ITT) population will be the main population for the efficacy variables. If the difference between the ITT and safety populations is 5 or fewer patients, all analyses will be based only on the safety population.

Estimates for the survival function for PFS, OS, and DoR will be obtained by the Kaplan-Meier approach.

The analysis of ORR will be assessed by best overall response (BOR), defined as a complete or partial response determined on two consecutive investigator assessments  $\geq 4$  weeks apart in patients with measurable disease at baseline. BOR rate will be defined as the percentage of patients who have a complete or partial response as their BOR. Patients without a post-baseline tumor assessment will be considered non-responders. The number and proportion of responders and non-responders will be presented with the corresponding Clopper-Pearson 95% CI.

DCR will be defined as the percentage of patients with a BOR of CR, PR, or SD and will be presented along with the 95% Clopper-Pearson CI.

Analyses on the PRO instruments will include summary statistics and change (absolute and percentage) from baseline, in addition to the time to event, such as time to deterioration, analysis.

## 6.6 SUBGROUP ANALYSES

Key safety and/or efficacy parameters will also be analyzed by the following subgroups:

- ECOG Performance status: 0–1 vs. 2
- Presence of CNS metastases at baseline: yes vs. no
- Renal impairment at study entry: yes vs. no
- Patient requiring dialysis: yes vs. no
- HIV status: negative vs. positive
- History of autoimmune disease: yes vs. no
- Progression on, or within 12 months of, prior platinum-based treatment: yes vs. no
- Concomitant steroid treatment ongoing at baseline: yes vs. no
- History of non-urothelial urinary tract carcinoma histology: yes vs. no
- Previous lines of cancer therapy (1 vs. 2 vs. 3)
- Age-adjusted Charlson comorbidity index (AACI):  $\leq 11$  vs.  $> 11$
- PD-L1 expression: low vs. high (cut-offs to be defined)
- Region (grouping countries into regions will be specified in the Statistical Analysis Plan)

All subgroup analyses will be based on the same methods as overall analyses of the primary and secondary variables. In addition, graphical displays such as forest plots will be used to descriptively visualize the homogeneity of key safety and efficacy parameters (proportions and 95% CI, or KM medians and corresponding 95% CI, as applicable will be displayed) across different levels of the pre-specified subgroup variables.

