Given the high unmet need for new therapies for advanced bladder cancer, it is of considerable interest to evaluate atezolizumab in a population of bladder cancer patients that mimics more closely a standard clinical population. As a first step in this process, the primary objective of Study MO29983 will be to analyze the safety of atezolizumab in a population of bladder cancer patients that includes patients who would have been screened out of many of the previous studies. The large majority of eligibility criteria in Study MO29983 remain unchanged from earlier trials and the safety of participants remains the highest priority. However, a small number of criteria have been broadened:

- Patients with a baseline ECOG performance status of 2 will now be eligible for enrollment, in addition to patients with ECOG performance statuses of 0 and 1
- CNS metastases will be allowed at baseline, if stable
- Patients with a renal clearance of  $\geq 15$  mL/min (rather than  $\geq 30$  mL/min) and/or a history of renal failure will be allowed in the study
- Prior treatment with non-platinum regimens will be allowed
- Patients with CNS metastases will be allowed to receive steroid treatments if the dose of prednisone is  $\leq 20$  mg/day (or equivalent)
- Patients with underlying controlled and stable autoimmune diseases will be allowed
- Patients with non-urothelial carcinoma of the urinary tract will be permitted to enroll in the trial

- Patients with HIV will be eligible, based on evidence suggesting that the PD-L1/PD-1 pathway may be operative in HIV infection and that PD-L1/PD-1 inhibition may have a role in reducing viral load

In addition to assessing safety, the current study will have secondary objectives to assess response and patient-reported outcomes, which will further advance the understanding of atezolizumab therapy in patients with cancer of the urinary tract. Finally, in exploratory analyses, the study will assess PD-L1 prevalence in tumor tissue using an IHC assay and will correlate a panel of biomarkers with efficacy and safety outcomes. These studies will continue to expand our understanding of atezolizumab and lay the groundwork for future clinical trials.

For additional rationale statements explaining the current study design, please refer to Section 3.3.

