4.4.5 Subgroup Analyses

Secondary efficacy endpoints are also analyzed by the following subgroups:

- ECOG Performance status: 0–1 vs. 2
- Presence of CNS metastases at baseline: yes vs. no

- Renal impairment at study entry: yes vs. no
- Creatine clearance at study entry (mL/min): 15-<30 vs 30-<60 vs >=60
- Sex: female vs. male
- HIV status: negative vs. positive
- Patients aged ≥ 65 years: yes vs. no
- Patients aged ≥ 70 years: yes vs. no
- Patients aged ≥ 75 years: yes vs. no
- Patients aged ≥ 80 years: yes vs. no
- Patients aged 65-<75 vs 75-<80 vs ≥ 80
- History of autoimmune disease: yes vs. no
- Progression on, or within 12 months of, prior platinum-based treatment: yes vs. no
- Concomitant steroid treatment ongoing at baseline: yes vs. no
- History of non-urothelial or mixed urinary tract carcinoma histology: yes vs. no
- Tumor location: Ureter vs Renal Pelvis vs all UTUC (Ureter or Renal Pelvis) vs Bladder
- Prior Lines of Treatment for Metastatic Disease (0 vs 1 vs. 2 vs. 3)
- Age-adjusted Charlson comorbidity index (AACI): ≤ 11 vs. > 11
- PD-L1 expression: IC2/3 vs. IC0/1
- PD-L1 expression by IHC Class: IC0 to IC3
- IMvigor211-like patients: yes vs. no
- Region: Australia/Canada/Western Europe vs Eastern Europe vs Other regions

All subgroup analyses are based on the same methods for statistical analyses of the respective secondary efficacy endpoint. Graphical displays such as forest plots are used to visualize the homo-/heterogeneity of secondary efficacy endpoint results across different levels of the subgroups defined above (proportions and 95% CI, or KM medians and corresponding 95% CI as applicable).

The subgroup PD-L1 expression will be derived from the percentage of tumor area infiltrating immune cells as follows:

IC=0 (<1%), IC=1 ($\geq 1\%$ - <5%), IC=2 ($\geq 5\%$ - <10%), IC=3 ($\geq 10\%$).

The subgroup “IMvigor211-like patients” is defined as follows:

Patients with:

- ECOG Performance status: 0–1
- Presence of CNS metastases at baseline: no
- Renal impairment at study entry: no
- Patient with renal dialysis reported at baseline: no
- HIV status: negative
- History of autoimmune disease: no

- Progression on, or within 12 months of, prior platinum-based treatment: yes
- Concomitant steroid treatment ongoing at baseline: no
- History of non-urothelial or mixed urinary tract carcinoma histology: no
- Prior Lines of Treatment for Metastatic Disease: 0 or 1 or 2
- Patients aged ≥ 65 years: indifferent

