- Number of death events, overall and by primary cause of deaths, occurrence of an autopsy, number of death events within 30 days/ later than 30 days to 90 days and later than 90 days after first study treatment administration, number of death events within 30 days/ later than 30 days to 90 days and later than 90 days after last study treatment administration
- Number of death events by number of cycles started (1 cycle, 2 cycles, 3 cycles, 4 cycles, 5 cycles or more and broken down by number of days since last dose: ≤ 30 days, $>30 - \leq 90$ days or >90 days) and by primary cause of death and occurrence of an autopsy. A death event will be associated with the number of cycles the patient received, a cycle being counted when dose >0 . A summary table and the corresponding figure will be provided.

By-patient listings based on the safety population will be provided for the following types of AEs:

- TEAEs and AEs who do not meet the criteria of TEAEs
- AEs of special interest
- AEs leading to permanent treatment discontinuation
- SAEs
- Fatal AEs (i.e. grade 5 AEs)

In addition, a by-patient listing of death case will be provided based on the Safety Population. Deaths events will be categorized in days since first dose and days since last dose: ≤ 30 days, $>30 - \leq 90$ days or >90 days in this listing.

In the above listings, information relative to the following subgroups of interest will be included:

- ECOG Performance status: 0–1 vs. 2 (the category 2 includes patients who recorded status 2 at screening but 3 at baseline)

- Progression on, or within 12 months of, prior platinum-based treatment: yes vs. no
- Concomitant steroid treatment ongoing at baseline: yes vs. no
- History: non-urothelial or mixed urinary tract carcinoma histology vs urothelial
- AACI: ≤ 11 vs. > 11
- Renal impairment at study entry: yes vs. no
- Sex: female vs. male
- HIV status: negative vs. positive
- History of autoimmune disease: yes vs. no
- Presence of CNS metastases at baseline: yes vs. no
- Patients: < 65 years vs. ≥ 65 years
- Patients: < 70 years vs. ≥ 70 years
- Patients: < 75 years vs. ≥ 75 years
- Patients: < 80 years vs. ≥ 80 years
- Prior Lines of Treatment for Metastatic Disease: 0 vs 1 vs. 2 vs. 3
- PD-L1 expression: IC2/3 vs. IC0/1
- PD-L1 expression: IC0 to IC3
- IMvigor211-like patients: yes vs. no
- Regions: Australia/Canada/Western Europe vs Eastern Europe vs Other regions

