In addition, the AE summary table described previously in this section will be repeated for each of the above subgroups.

A by-patient listing of immune-related thyroid disorders on the safety population will also be provided.

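### The SAP plans no separate output for the protocol's pre-specified dialysis subgroup and gives no reason for leaving it out

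*Protocol*

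**What the plan says.** Protocol 6.6 introduces its 13 subgroups with "Key safety and/or efficacy parameters will also be analyzed by the following subgroups". Dialysis, "Patient requiring dialysis: yes vs. no", has its own line directly after renal impairment.

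SAP 4.4.5 opens its efficacy list with "Secondary efficacy endpoints are also analyzed by the following subgroups" and gives 22 entries. Two are renal: impairment yes or no, and "Creatine clearance at study entry (mL/min): 15-<30 vs 30-<60 vs >=60". Neither is dialysis.

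SAP 4.6.2 names 19 subgroups for the safety listings and then states "In addition, the AE summary table described previously in this section will be repeated for each of the above subgroups". Its only renal entry is "Renal impairment at study entry: yes vs. no".

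SAP 4.3 defines renal impairment as Cockcroft-Gault clearance at baseline below 30 mL/min, without reference to dialysis. It also derives a baseline dialysis flag. For patients included under protocol version 5 or higher, the flag is Yes if dialysis is reported at Screening or Cycle 1 Day 1. For everyone included under an earlier version it is No, whatever was reported. Among subgroups, the flag appears only as a condition of the IMvigor211-like definition in SAP 4.4.5: "Patient with renal dialysis reported at baseline: no".

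**The concern.** Protocol 6.6 leaves the choice between safety and efficacy open, but its wording does not allow for neither. Followed as written, the SAP produces neither for dialysis. It keeps a counterpart of every other protocol subgroup and adds several more (sex, age cuts, tumour location, clearance bands). Elsewhere it does comment on a protocol rule that turned out not to apply, namely the five-patient ITT rule in SAP 4.1.5. On dialysis it is silent.

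The primary objective is safety, and Protocol 1.4 explains that the trial looks at patients whom earlier studies would have screened out. Severe renal disease belongs to that aim. At stake is a descriptive safety table for a group the protocol marked for separate analysis, and an undocumented departure from the protocol. No hypothesis test, error rate or sample size is involved.

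**Working it through.** **1. List comparison.** Each protocol subgroup was checked against both SAP lists.

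| Protocol 6.6 subgroup | SAP 4.4.5 (22 entries) | SAP 4.6.2 (19 entries) |
|---|---|---|
| ECOG status | yes | yes |
| CNS metastases | yes | yes |
| Renal impairment | yes | yes |
| **Dialysis** | **no** | **no** |
| HIV status | yes | yes |
| Autoimmune disease | yes | yes |
| Progression on or after platinum | yes | yes |
| Steroids at baseline | yes | yes |
| Non-urothelial histology | yes, mixed added | yes, mixed added |
| Prior lines | yes, 0 to 3 | yes, 0 to 3 |
| AACI | yes | yes |
| PD-L1 | yes | yes |
| Region | yes | yes |

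Twelve of 13 have a counterpart in both lists. Dialysis is in neither, nor in the pairwise-association list at the end of SAP 4.4.5. The baseline bullets in SAP 4.3 do not name a dialysis count.

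**2. Can renal impairment stand in for dialysis?** The SAP 4.3 formula for a man is (140 − age) × weight / (72 × creatinine). The patients below are assumed, for illustration only:

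- Age 70, 75 kg, creatinine 3.0 mg/dL: 70 × 75 / (72 × 3.0) = 5250 / 216 = 24.3 mL/min, classed as impaired.
- Age 60, 90 kg, creatinine 3.3 mg/dL: 80 × 90 / (72 × 3.3) = 7200 / 237.6 = 30.3 mL/min, classed as not impaired.

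A dialysis patient could therefore fall on either side of the cut. Below 30 mL/min, the patient is pooled with non-dialysis patients. At 30 or above, the patient is grouped with the unimpaired. In neither case can a dialysis rate be read off. The IMvigor211-like definition itself lists no renal impairment and no dialysis as two separate conditions. The comorbidity worksheet (Protocol Appendix 9, item 8) counts dialysis as severe renal disease, but SAP 4.3 summarises only the total score.

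**3. Precision of a restored row.** The exact limits are the 2.5% quantile of Beta(x, n − x + 1) and the 97.5% quantile of Beta(x + 1, n − x).

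The plan's own figure comes first. For x = 5 and n = 1000 these give 0.16% and 1.16%, with half-width (1.16 − 0.16) / 2 = 0.50 points, as stated in Protocol 6.1. All nine rows of Protocol Table 6 reproduce.

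For x = 0 the upper limit reduces to 1 − 0.025^(1/n). The documents do not give the number of dialysis patients, so n is assumed:

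| Assumed n | Upper 95% limit, no events | Largest half-width at any count |
|---|---|---|
| 5 | 52.2% | ±40.0 points |
| 10 | 30.8% | ±31.3 points |
| 20 | 16.8% | ±22.8 points |
| 50 | 7.1% | ±14.5 points |

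**The case against.** The strongest reply is that little is lost. Dialysis patients remain in every overall safety table and in the by-patient listings of AEs, SAEs, fatal AEs and deaths. Many would fall in the impaired group, where their results are diluted but still present. With a handful of patients, an upper limit of 52% or 31% would settle no safety question. Because the flag is derived, crude counts could be obtained on request.

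Much of this stands, and it sets the size of the point. It does not explain the omission. The SAP gives no argument from small numbers, and it keeps CNS metastases, which Protocol 1.4 describes as rare. All analyses are descriptive, so imprecision is a reason to show a count and an interval, not to show nothing. The listings in SAP 4.6.2 carry the named subgroup information, and dialysis is not among it.

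A reader might infer that the trial deliberately admitted dialysis patients. The documents do not go that far. Protocol 1.4 says patients with a "history of renal failure will be allowed in the study", which is not the same as dialysis, and no eligibility criterion names dialysis. The operative renal criteria are a calculated clearance of at least 15 mL/min (inclusion criterion 10) and exclusion for a renal disorder indicating need for transplant (exclusion criterion 9). The subgroup line shows only that such patients were anticipated.

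**Conclusion.** The point holds as an unexplained discrepancy between protocol and SAP. A pre-specified subgroup has no planned separate output, and the available renal subgroups cannot replace it. It is minor: the primary analysis, sample size and overall safety results are unaffected.

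It is tempting to conclude that the trial will have no safety result for dialysis patients. That is too strong. The SAP is a plan, these patients contribute to the overall results, and what is missing is a separate tabulation.

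How much that tabulation would tell depends on a number the documents do not give. The limits of 52.2%, 30.8% and 16.8% rest on assumed groups of 5, 10 and 20 with no event. How many dialysis patients have a calculated clearance of 30 mL/min or more is also unknown; the worked cases show only that it is possible.

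**What to change.** - **Safety (SAP 4.6.2):** add dialysis yes vs. no to the subgroup list. Give the number of patients, the AE/death summary table with Clopper-Pearson intervals, and a dialysis flag in the AE, SAE and death listings.
- **Efficacy (SAP 4.4.5):** add the subgroup if numbers allow. If not, state there why efficacy is not shown.
- **Flag (SAP 4.3):** base it on reported dialysis whatever the protocol version, or footnote each output that the flag is set to No for patients included under versions below 5. Without this, a restored subgroup could place patients with reported dialysis in the No row.

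The variable and the subgroup programs are already planned, so the work is one more subgroup and a revised derivation or a footnote. The downside is one small, imprecise descriptive table, to be labelled as such.

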## 6.7 BIOMARKER ANALYSES

The biomarker objectives of this trial include correlating clinical benefit (e.g., OS, PFS, ORR, DCR, and DoR) with baseline expression levels of various biomarkers and profiles including, but not limited to, tumor PD-L1 as assessed by IHC. Biomarkers and biomarker profiles may be assessed using various methodologies including, but not limited to, IHC (single and multiplex e.g., PD-L1 expression and immune cell infiltration analyses), RNA and DNA analysis (e.g., mutation and expression analyses).

Different statistical methods will be used for the exploratory biomarker analyses, for example (but not limited to): frequencies and proportions (including 95% CI) of binary variables like response rates in different biomarker profile groups, and exact binomial tests to evaluate the associations of biomarkers and biomarker profiles with binary endpoints like objective response rates. Estimations of time-to-event outcomes in different biomarker subgroups (including duration of response, progression-free survival, and overall survival) might be analyzed by Kaplan-Meier methods; medians and corresponding 95% CI will be reported by biomarker subgroups. For continuous

biomarkers, such as tumor mutation burden, sliding window analyses might be used to determine the ideal cut-off.

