### **1.3.3 Efficacy**

[figure not shown]
IMvigor 210 (Study GO29293) is a single-arm, open-label, Phase II study to assess the clinical benefit of atezolizumab as a single agent in patients with locally advanced or metastatic UC. The co-primary endpoints of the study were IRF-assessed ORR according to RECIST v1.1 and investigator-assessed ORR according to modified RECIST criteria. Results from Cohort 2, which contained patients whose disease had progressed after previous platinum-based chemotherapy (see Section 1.3.2), were recently published ([Rosenberg et al. 2016](#)).

Between 13 May 2014, and 19 Nov 2014, 486 patients were screened and 316 patients were enrolled into IMvigor 210. Of these, 311 patients received atezolizumab treatment (five enrolled patients later did not meet eligibility criteria and were not dosed with study drug).

The primary analysis (data cutoff 05 May 2015) showed that treatment with atezolizumab resulted in significantly improved ORR for each pre-specified immune cell group when compared with a historical control ORR of 10% (IC2/3: 27% [95% CI 19–37%],  $p<0.0001$ ; IC1/2/3: 18% [13–24%],  $p=0.0004$ ). The same was true for the entire population of patients (15% [11–20],  $p=0.0058$ ). With longer follow-up by independent review (data cutoff 14 September 2015), ORRs were 26% (95% CI 18–36%) in the IC2/3 group, 18% (13–24%) in the IC1/2/3 group, and 15% (11–19%) overall in all 310 patients. Ongoing responses were recorded in 38 (84%) of 45 responders after a median follow-up of 11.7 months (95% CI 11.4–12.2 months).

Further details of the response to atezolizumab in IMvigor 210 are presented in [Figure 1](#).

**Figure 1. Change in Sum of the Diameters Over Time by Best Response in the PD-L1 IC2/3 group and Overall Survival in PD-L1 Immune Cell Groups**

IC = immune cell

Note: The above figure presents the percentage change in the sum of longest diameters by IRF-assessed RECIST v1.1 in the IC2/3 group by (A) responders, (B) patients with stable disease, and (C) patients with progressive disease. Patients without a measurable baseline tumor assessment or without post-baseline tumor measurements were not included. (D) Kaplan-Meier overall survival curves for the IC0, IC1, and IC2/3 groups.

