## 6.1 DETERMINATION OF SAMPLE SIZE

This is a single-arm safety study. There is no formal statistical hypothesis and all analyses will be descriptive. The results for the primary safety variables will be presented via percentages and corresponding 95% Clopper-Pearson CIs.

A sample size of approximately 1000 patients is planned for this study. The precision of rare AE incidence estimates presented by two-sided exact 95% Clopper-Pearson CIs are shown in [Table 6](#).

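### Protocol 6.7 names a test that in its usual form does not compare biomarker groups, and allows a data-chosen cut-off without correction or validation (low severity; exploratory analyses)

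*Protocol*

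**What the plan says.** Protocol 6.7 introduces its methods as an open list: "Different statistical methods will be used for the exploratory biomarker analyses, for example (but not limited to"). The list has four elements: proportions with 95% confidence intervals by biomarker group, "exact binomial tests to evaluate the associations of biomarkers and biomarker profiles with binary endpoints like objective response rates", Kaplan-Meier estimates with medians and intervals by biomarker subgroup, and a remark on continuous markers such as tumor mutation burden, for which "sliding window analyses might be used to determine the ideal cut-off".

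The section gives no null value, sidedness or significance level for the binomial test. It gives no window width, search range, selection criterion, correction or validation for the cut-off.

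Three other places matter:

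- Protocol 6.1 says of the study as a whole: "There is no formal statistical hypothesis and all analyses will be descriptive".
- Protocol 6.6 leaves the PD-L1 grouping open, "PD-L1 expression: low vs. high (cut-offs to be defined"), but SAP 4.4.5 closes it. There the groups are IC2/3 against IC0/1, and IC0 to IC3, with percentage boundaries written down.
- SAP 4.6.6 marks biomarker endpoints as not applicable, so it neither repeats nor repairs the methods in 6.7.

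**The concern.** Association between a marker and response is a question about two or more groups. The ordinary exact binomial test has one sample and a reference value that is known without error. An analyst who follows 6.7 literally has to supply that reference. The two obvious choices are an outside rate, which answers a different question, and the other group's observed rate, which ignores that group's sampling error.

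The cut-off remark raises a separate problem. A threshold picked because it separates outcomes best will show separation in the data that picked it, even for a marker unrelated to outcome. This affects estimates and intervals as well as p-values.

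Relating biomarkers to safety and efficacy is a stated objective (Protocol 2.4), and Protocol 3.3.4 wants to learn how PD-L1 might serve as a predictive marker. False leads would be carried into later work. No primary or secondary endpoint is affected.

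**Working it through.** Section 6.7 states no power, error rate or sample size, so there is no planned figure to reproduce.

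**Inputs**
- Planned total: "A sample size of approximately 1000 patients is planned for this study" (Protocol 6.1). The number with usable biomarker data is not stated; I assume 300 to 1000.
- Response rate: no rate is assumed for this study. I use 15% in both groups, from the earlier phase II study in Protocol 1.3.3, "15% (11–19%) overall in all 310 patients".
- Two-sided 5% level (assumed). The group sizes below are illustrative and not from the documents.

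**Step 1: one group tested against the other's observed rate.** The test takes the variance of the difference as p(1−p)/n1. The true variance is p(1−p)(1/n1 + 1/n0), larger by the factor 1 + n1/n0. The real size is therefore about 2Φ(−1.96/√(1 + n1/n0)):

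- 280 against 720: √1.389 = 1.179; 1.96/1.179 = 1.66; size 9.6%
- 500 against 500: √2 = 1.414; 1.96/1.414 = 1.39; size 16.6%
- 720 against 280: √3.571 = 1.890; 1.96/1.890 = 1.04; size 30.0%

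Simulating the exact test itself gives about 8–9%, 16% and 30%. Fisher's exact test on the same data gives 4–5%.

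**Step 2: other reference values.**
- Against a fixed 10% (the historical control in Protocol 1.3.3), a group with a true rate of 15% is rejected with probability 72% (n = 280), 93% (n = 500) and 98% (n = 720). Both groups tend to reject although the marker does nothing. Section 6.7 does not propose this reference.
- Against the overall observed rate, size is 0–3.4%, which is conservative.
- A conditional form compares a group's share of the responders with its share of the patients: given R responders in total, X1 is roughly Binomial(R, n1/N). Its size is about 3%. It is conservative, but it does test association.

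**Step 3: searched cut-off.** For an unrelated continuous marker and a cut after the k-th ranked patient, take z² = (p̂1 − p̂0)² / [p̂(1−p̂)(1/k + 1/(N−k))]. Choose the k with the largest z² and compare it with 3.84. Last column: how often the ordinary 95% interval for the selected difference contains the true value, zero.

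| Cut-offs searched | False association, N = 1000 | Mean spurious gap in response rate, N = 1000 / N = 300 (points) | Coverage of 95% CI, N = 1000 |
|---|---|---|---|
| Quartiles | 12% | 3.2 / 5.7 | 87% |
| Deciles | 25% | 4.6 / 8.5 | 75% |
| 5-percentile steps, 10th–90th | 30% | 4.8 / 8.9 | 69% |
| Every value, 25th–75th | 30% | 4.1 / 7.4 | 70% |
| Every value, 10th–90th | 46% | 5.6 / 9.9 | 54% |
| Every value, 5th–95th | 54% | 6.9 / 12.1 | 44% |

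These are Monte Carlo results with 5,000 to 10,000 replicates; repeat runs agree to within about 2 points. The Miller–Siegmund approximation for a maximally selected chi-square gives 31% (25th–75th), 49% (10th–90th) and 62% (5th–95th): the same order, and higher for wide searches.

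A single pre-specified median split has size 4.5–5.3%. To hold 5% overall at N = 1000, the smallest p-value would have to fall below about 0.0028 (every value, 10th–90th) or 0.0056 (5-percentile steps).

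**The case against.** The strongest reply is that 6.7 is deliberately loose. Its list is illustrative, sliding windows only might be used, and no test at the selected cut-off is announced. The analyses are exploratory, in a single-arm safety study without hypotheses. A sliding window often means estimating outcome in overlapping bands of the marker, which is not the maximum over cut-offs simulated here. All of this stands, and it limits both the severity and the precision of any inflation figure.

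Four stronger readings are tempting, and the documents do not support them:

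- A reader might infer that an exact binomial test cannot test association. The conditional form on responders does so. The text does not say which form is meant, so the criticism is of the usual one-sample form.
- A reader might infer that 6.7 offers only these two methods. It also names group proportions and Kaplan-Meier estimates, and it excludes nothing.
- A reader might infer that 6.7 is the entire biomarker plan. For PD-L1, SAP 4.4.5 fixes the groups in advance and analyses the secondary efficacy endpoints by them with intervals and forest plots.
- A reader might infer a single false-positive rate for the cut-off search. Without a stated range, grid and criterion, only a span conditional on assumptions can be given.

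Two parts of the reply do not stand. Exploratory status does not make a one-sample test compare groups. Nor does the absence of a p-value rescue the searched cut-off, because the coverage column shows that plain estimates and intervals mislead too. The one-sample reading is also not far-fetched: SAP 4.4.5 declares associations between subgroups by setting a confidence limit for one of them against the whole-population percentage, treated as known.

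**Conclusion.** The point holds, at low severity. The test named for biomarker-response association does not, in its usual form, compare groups. If the other group's observed rate is used as the reference, the type I error is about 8–9%, 16% or 30% for the three splits shown, against 4–5% for Fisher's exact test. These figures assume a 15% response rate in both groups and illustrative group sizes.

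The cut-off point is conditional. If a sliding-window search picks a threshold and the same data are then used to test or estimate at it, an unrelated marker looks associated in about 12% to 54% of cases at nominal 5%, with an average spurious gap of roughly 3–12 points. That span depends on the range and fineness of the search and on 300 to 1000 evaluable patients. The protocol does not say that this second step will be taken; it gives no safeguard if it is. PD-L1 as grouped in SAP 4.4.5 is outside the cut-off problem. Tumor mutation burden and other continuous markers are not.

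**What to change.** In Protocol 6.7:

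1. Replace the exact binomial test with Fisher's exact test, or with logistic regression reporting an odds ratio and 95% confidence interval.
2. Analyse continuous markers as continuous, for example in logistic or Cox models with a spline.
3. For any cut-off chosen from the data, state the search range and selection criterion. Report a p-value adjusted by permutation or by the maximally selected statistic, give cross-validated estimates, and label the result hypothesis-generating.
4. State that PD-L1 uses the groups fixed in SAP 4.4.5.

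The cost is a few sentences of wording and standard software procedures; no data collection changes. The downside is fewer nominally positive findings.
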